Diagnostic Stewardship for Ventilator Associated Pneumonia

Description of Outcomes and Statistical Analysis Plan

NCT05989269

August 11, 2023

Specific Aim 1: In a cluster-randomized crossover trial among 6 ICUs across 3 medical centers, evaluate the impact of a VAP diagnostic stewardship intervention on antibiotic use, VAP diagnoses, and adverse events.

Hypothesis: We expect a reduction in unnecessary antibiotics for VAP and in VAP clinical diagnoses in the intervention vs. control periods across all sites, without an increase in adverse events.

Primary Outcome: The primary efficacy outcome is reduction in proportion of unnecessary antibiotic therapy for presumed VAP in the intervention (modified reporting) period compared to control (standard reporting period), among patients not meeting clinical criteria for pneumonia and with growth of one or more organism(s) not considered normal upper respiratory flora.

Antibiotic action based on index culture result will be classified as follows:

- a) Not on empiric antibiotic(s), new antibiotic started based on index respiratory culture result, completed course for VAP
- b) Not on empiric antibiotic(s), no new antibiotics initiated based on culture result
- c) On empiric antibiotic(s), changed based on index respiratory culture, completed course for VAP
- d) On empiric antibiotic(s), continued without change following index respiratory culture, completed course for VAP
- e) On empiric antibiotic(s), antibiotics discontinued based on culture results
- f) On empiric antibiotics(s), but this therapy was not directed at the results of the index respiratory culture, and was not directed towards VAP

For patients where culturing was deemed inappropriate, antibiotic use in categories a, c, and d will together be considered “unnecessary antibiotic therapy for presumed VAP”

Note: Multiple respiratory cultures from the same patient may be eligible for intervention i.e., modified reporting during the intervention period. However, clinical outcomes linked to an “index respiratory culture” will be assessed using a single randomly selected respiratory culture from each included patient.

Secondary outcomes are as follows:

1. Antibiotic consumption outcomes: The following three outcomes will be measured to understand the impact on antibiotic use in ICU patients

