 - a. Duration of antibiotic therapy: The duration of antibiotic therapy for possible or presumed VAP among patients who underwent intervention during the intervention period and among patients eligible for intervention in the control period will be compared. Duration of antibiotic therapy will be collected for all categories above (except b), and defined as uninterrupted days of therapy, irrespective of the number of different antibiotics, for the same episode of presumed VAP, assessed at discharge or day 28 whichever occurs first. For patients in category b, duration will be zero.
 - b. Antibiotic consumption during study intervention and control periods will be collected as antibiotic days of therapy (DOTs) as defined by CDC (Centers for Disease Control) NHSN as number of days that patients receive an antibiotic agent during a calendar day. The DOT for a given patient receiving multiple antibiotics on the same calendar day will

be the sum of the DOT for each antibiotic. This will be standardized to patient census of 1,000 patient days.

- i. Unit-level total antibiotic days of therapy (DOT) per 1,000 ICU patient-days: These data will be obtained from the hospital antimicrobial stewardship programs and will be compared in aggregate between the intervention and control periods for all study ICUs combined, and by hospital.
 - ii. Unit-level respiratory antibiotic DOT: This will be captured from the EMR by counting antibiotics that are ordered for “respiratory infection” indication starting at day 3 or later of ICU stay and expressed as days of therapy per 1,000 ICU patient-days. We will validate this outcome by chart review of a small sample of patients. These will be compared in aggregate between the intervention and control periods for all study ICUs combined, and by hospital.
2. Clinical diagnoses of VAP within 7 days after the index culture - measurement of this outcome will help understand how modification of reporting would influence the likelihood of a patient receiving a diagnosis of VAP. Because there are no consensus definitions for VAP, we will use the treating clinician’s documentation of pneumonia or VAP and treatment for those conditions to capture this outcome. The clinical diagnosis of VAP is an intermediate outcome that precedes the endpoint of antibiotic use. Clinical diagnoses of tracheobronchitis within 7 days after the index culture will also be recorded.

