 - a. We will perform a sensitivity analysis of the impact on antibiotic use outcomes after excluding patients diagnosed with tracheobronchitis within 7 days of index culture. The hypothesis is that the intervention will have limited impact on those diagnosed and treated for ventilator-associated tracheobronchitis, and thus, we may see a larger difference between intervention and control when excluding patients with diagnoses of tracheobronchitisVentilator-free days: Ventilator-free days is defined as the number of calendar days within 28 days after the index respiratory culture on which the patient was not mechanically ventilated. Any patient dying within 28 days of the index respiratory culture collection will be assigned zero ventilator-free days. Ventilator-free days will be compared between the intervention and control periods for all study ICUs combined, and by hospital.
3. Rate of requests for complete reports in the intervention period – these data are applicable in the intervention period only. This will be a primarily descriptive analysis to help us understand if the intervention worked as intended i.e., how frequently did clinicians still want the full report with organism identification despite the nudge to consider asymptomatic colonization.
4. Adverse event outcomes: Death, bacteremia, and septic shock (from any cause) within 7 days of the index culture order will be recorded as potential significant adverse events from a delayed or missed true VAP diagnosis or delay in initiation of appropriate antimicrobial therapy, similar to methods described by Daley et al.¹ Incidence of these events will be compared between intervention and control periods individually for each event, and as a combined adverse event outcome. Two-person adjudication will be used to determine whether the above events were attributed to the intervention, during the intervention period.

Statistical methods for Aim 1:

Descriptive analyses using the Wilcoxon rank-sum test for continuous variables and the chi-square or Fisher’s exact tests for categorical variables will be used to compare patient-level data across each intervention arm. Analyses will be conducted on an intention-to-treat basis and will account for the cluster-randomized crossover design to ensure correct type I error rates and confidence intervals (CIs). A significance level of 0.05 will be used for all statistical comparisons.

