Power and Sample Size: For the population of ICU patients for which ordering of a respiratory culture has been determined inappropriate and there is growth of one or more organism(s) not considered normal upper respiratory flora, we test the effect of the diagnostic stewardship intervention on the proportion of antibiotic prescription in a two-period cluster-randomized cross-over design, where an ICU forms a cluster. The outcome follows a binary distribution with 50% probability to receive antibiotic prescription in the control group (pC). In a conservative estimate, we expect that the intervention reduces the probability by $\Delta = 0.15$ (= pC – pI) percentage points. Assuming the within-cluster within-period correlation is $\rho = 0.06$ and the within-cluster between-period correlation is about $\eta = 0.054$ ^{2,3} a total sample size of $N = 350$ in 6 ICUs across both periods is needed to detect an effect of $\Delta = 0.20$ with 85% power, using a generalized linear mixed model with random cluster, period, and cluster-period interaction effect. The computed total N is equivalent to a mean of about 5 patients per ICU per month, which is feasible in our experience. Given the uncertainty in predicting the actual number of patients that will be eligible to receive the intervention per ICU during the fixed 6-month period, we calculated the power for varying range of effect sizes and total N (Table).

Option	Power	Proportion control	Proportion intervention	N patients eligible for intervention per ICU per period*	Within-cluster within-period rho	Within-cluster between-period rho	Total N
1.	90%	50%	35%	30	0.06	0.054	619
2.	85%	50%	35%	30	0.06	0.054	547
3.	80%	50%	35%	30	0.06	0.054	493

4.	90%	50%	30%	30	0.06	0.054	390
5.	85%	50%	30%	30	0.06	0.054	350
6.	80%	50%	30%	30	0.06	0.054	322
7.	90%	50%	25%	30	0.06	0.054	285
8.	85%	50%	25%	30	0.06	0.054	261
9.	80%	50%	25%	30	0.06	0.054	243

Cluster- and participant-level covariates at baseline will be reported within each intervention arm. Adjusted analysis of the primary outcome will be performed as needed to control for differences in possible influential factors between intervention arms at baseline.

Statistical Methods for Secondary outcomes:

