Generalized linear mixed models with a random cluster, period, and a cluster-period interaction modeling a negative binomial distribution will be used to compare the antibiotic duration count outcomes assessed at the participant-level (i.e., duration of therapy) between the intervention vs the control ICUs. The Wilcoxon rank-sum will be used to compare differences in antibiotic duration outcomes assessed at the ICU-level (total and respiratory antibiotic DOT) across intervention arm. Similar to the primary outcome model, generalized linear mixed model with random cluster, period, and cluster-period intervention effect will be used to compare other binomial participant-level outcomes (i.e., adverse events) across intervention arm. No adjustment for multiple comparisons will be made for secondary outcomes, therefore results should be considered exploratory.

Specific Aim 2: Evaluate overall impact of intervention including clinical and antibiotic outcomes using the "Desirability of Outcome Ranking (DOOR)/ Response Adjusted for Duration of Antibiotic Risk (RADAR)" methodology.

Aim 2a: Apply DOOR/RADAR methodology to measure outcomes of specific Aim 1

Hypothesis: We expect better overall patient outcomes (better DOOR ranking, accounting for duration of antibiotic use) in the intervention vs. control period.

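### Unit-level antibiotic DOT is compared with an unpaired rank-sum test although each of the 6 ICUs supplies both arms, so the analysis drops the ICU pairing and ignores period

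*SAP*

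**What the plan says.** The SAP describes the design under Specific Aim 1 ("In a cluster-randomized crossover trial among 6 ICUs across 3 medical centers") and under Power and Sample Size ("two-period cluster-randomized cross-over design, where an ICU forms a cluster"). Every ICU therefore has one control and one intervention period. Statistical methods for Aim 1 promises that analyses "will account for the cluster-randomized crossover design to ensure correct type I error rates and confidence intervals".

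Statistical Methods for Secondary outcomes follows that promise for patient-level antibiotic duration: "Generalized linear mixed models with a random cluster, period, and a cluster-period interaction modeling a negative binomial distribution". The patient-level binary outcomes get a similar model. The next analysis departs from it: "The Wilcoxon rank-sum will be used to compare differences in antibiotic duration outcomes assessed at the ICU-level (total and respiratory antibiotic DOT"), compared across intervention arms. No ICU, pairing or period term is mentioned.

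Item 1b of the secondary outcomes says of DOT: "This will be standardized to patient census of 1,000 patient days". It adds that the rates "will be compared in aggregate between the intervention and control periods for all study ICUs combined, and by hospital". This suggests one pooled rate per ICU-period, but the SAP never states which values are ranked. It does state the standing of these outcomes: "No adjustment for multiple comparisons will be made for secondary outcomes, therefore results should be considered exploratory".

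**The concern.** A rank-sum test treats the intervention and control values as coming from different, unrelated units. Here they come from the same six ICUs. ICUs commonly differ in antibiotic use for lasting reasons such as case mix, and a crossover is chosen so that each ICU can serve as its own control. The rank-sum test leaves those stable differences in the error term. It also has no means of removing a change in antibiotic use between the first and second period.

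DOT is the plan's only unit-level measure of antibiotic use. A consistent fall across the six ICUs could be reported as no detectable change, and a reader could take that as evidence that modified reporting did not affect overall ICU antibiotic use. The test as specified also yields no effect estimate with an interval.

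**Working it through.** The SAP gives no power, effect size, variance or correlation for DOT, so there is no figure of its own to reproduce. What follows is an illustration under stated assumptions.

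**Inputs from the SAP.** 6 ICUs, two periods, each ICU in both arms, significance level 0.05.

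**Assumed.** Two-sided testing; one rate per ICU-period; normal values with SD 1; correlation *r* between an ICU's two periods; a true fall of 0.75 SD; 3 ICUs per sequence; no period shift unless stated.

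**Rank-sum test, 6 v 6.** There are C(12,6) = 924 equally likely rank arrangements under independence. The largest two-sided rejection region not above 0.05 is U ≤ 5 or U ≥ 31, with probability 2 × 19/924 = 0.041. Its behaviour under pairing was obtained by simulation.

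**Period-adjusted within-ICU t-test.** Twelve values less 6 ICU, 1 period and 1 treatment parameters leave 4 df. The treatment effect has variance 2(1 − *r*)/6, so the noncentrality is 0.75/√(2(1 − *r*)/6):
- *r* = 0: 0.75/0.577 = 1.30
- *r* = 0.5: 0.75/0.408 = 1.84
- *r* = 0.9: 0.75/0.183 = 4.11

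Power comes from the noncentral t distribution.

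| Correlation *r* | Rank-sum type I error | Rank-sum power | Within-ICU t-test power |
|---|---|---|---|
| 0 | 4% | 18% | 17% |
| 0.3 | 2% | 16% | 22% |
| 0.5 | 1% | 14% | 29% |
| 0.7 | 0.4% | 12% | 44% |
| 0.9 | 0.03% | 11% | 86% |

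**Period shift, equal sequences.** A 1 SD shift adds noise to the unpaired comparison and cuts rank-sum power to 12%, 7% and 2% at *r* = 0, 0.5 and 0.9. The period-adjusted test is unchanged.

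**Period shift, unequal sequences.** The shift now also displaces the raw arm contrast.
- 2 v 4: displacement (4 − 2)/6 = 0.33 SD. At *r* = 0.5, rank-sum power is 21% or 2%, depending on whether the shift favours or opposes the effect, against 7% for 3 v 3. Type I error stays below 5%.
- 1 v 5: displacement (5 − 1)/6 = 0.67 SD. Type I error is 12% at *r* = 0 and 7% at *r* = 0.5.

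**Several values per ICU-period.** Suppose 6 values per ICU-period (36 v 36) are ranked as independent. Type I error then depends on the assumed ICU / ICU-by-period / residual variance shares: 1.3% at 0.5/0/0.5, 7% at 0.5/0.1/0.4 and 14% at 0.5/0.2/0.3.

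**A concrete case.** Assume control rates of 600, 700, 800, 900, 1000 and 1100, with a 10% fall in every ICU. All six ICUs move the same way, yet the rank-sum p-value is above 0.5. A signed-rank test on the six differences gives 2/64 = 0.031.

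**The case against.** **The stakes are modest.** These are two exploratory aggregate measures. Patient-level antibiotic duration, the more direct measure, already has a model with cluster and period terms. This stands and limits the weight of the point. The exploratory label, however, is given because there is no multiplicity adjustment. It does not justify a test that disregards the design.

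**The size is assumed.** This also stands. The contrast of 11% v 86% needs a correlation of 0.9. At 0 the within-ICU test gains nothing, and at 0.5 it reaches only 29%. The SAP's correlations for the primary outcome have a ratio of 0.054/0.06 = 0.90, which makes a high value plausible, but they concern a different outcome and do not establish it for DOT.

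**The rank-sum test might be meant in its valid crossover form**, comparing within-ICU period differences between the two sequences. The SAP says the comparison is across intervention arms, which does not fit. With 3 v 3 ICUs the smallest two-sided p-value would be 2/20 = 0.10, so that version could never reach 0.05.

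**A reader might infer that ignoring the pairing inflates false positives.** The SAP does not support that as a general claim. With one rate per ICU-period and equal sequences the error is in the other direction. The opposite claim, that the test can never exceed 5%, is also too strong: the 1 v 5 split with a period shift and the several-values case are counterexamples. The SAP states neither the sequence allocation nor the ranked unit, so neither can be ruled in or out.

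**Conclusion.** The point holds. The planned DOT test is inconsistent with the SAP's own description of the design and with its commitment to account for the crossover, and nothing elsewhere in the SAP repairs it.

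On the most natural reading (one rate per ICU-period, equal sequences), the consequence is a conservative test and lost power, growing with the between-period correlation: nothing at 0, about half the achievable power at 0.5 (14% v 29%) and most of it at 0.9 (11% v 86%). These figures rest on an assumed 0.75 SD fall, normal values and no period shift. With unequal sequences, a period shift additionally displaces the arm contrast.

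A reader might go further and conclude that the trial's main result is at risk. It is not: the primary outcome has its own mixed model, and the DOT outcomes are secondary and exploratory. The change should be made, but the plan does not stand or fall on it.

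**What to change.** In Statistical Methods for Secondary outcomes:

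1. State that each ICU contributes one pooled DOT rate per period (total DOT divided by patient-days), for total and for respiratory DOT.
2. Replace the rank-sum test with a within-ICU, period-adjusted analysis, and report the rate ratio with 95% CI as the main result. Two suitable examples are a linear model on log DOT rate with ICU, period and treatment effects (4 df), or a count model with a patient-day offset and a small-sample correction. The second is closer to the SAP's other models.
3. Show the by-hospital results descriptively. If each hospital has two ICUs (an assumption), the smallest possible two-sided rank-sum p-value is 2/6 = 0.33.

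A plain signed-rank test is a weaker repair. With 6 ICUs it reaches 0.05 only if all six move the same way (p = 0.031), and it does not adjust for period.

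The cost is one or two sentences, with no new data. The downsides are a modelling assumption that six ICUs can barely check, no gain if the between-period correlation is near 0, and limited power at moderate correlation. The log-rate example also weights ICUs equally whatever their patient-days.

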Strategy: We will determine the probability that a patient who received the intervention has a better outcome than a participant who received the standard treatment. The clinical outcome of a participant will be ranked according to the table, from most (lower rank) to least (higher rank) desirable outcome, to obtain a 5-level ordinal outcome. We will conduct pairwise comparisons of each intervention patient to each control patient using two rules: When comparing patients with different overall clinical outcomes, the patient with a better overall clinical outcome based on the ranks in the below Table (Table 2) is determined to have the better outcome. When comparing two patients who have the same rank based on overall clinical outcome, the patient with a shorter course of antibiotics has the better outcome. Therefore, clinical outcome outranks the duration of antibiotic use i.e., a patient with a worse clinical outcome cannot have a better rank than a patient with a better clinical outcome, regardless of the duration of antibiotics.⁴ The duration of antibiotic therapy for possible or presumed VAP in relationship to the index respiratory culture (see above) will be used as the antibiotic duration measure for this analysis. Note that some patients will be on antibiotic therapy for reasons other than VAP - category f above. Thus, our antibiotic use duration may be more conservative for RADAR than studies that only look at antibiotics for the specific clinical entity, but this strategy helps to avoid overestimating

the impact on ICU antibiotic use in general. We will plan to conduct a sensitivity analysis with duration of antibiotic use defined with and without category f.

Table 2. Proposed DOOR criteria rank ordered by desirability of outcome

Rank	Objective clinical outcome (must meet each criterion listed for rank)
1	Discharged home by day 14, and not readmitted between days 15-28
2	Discharged home by day 14 but readmitted between days 15-28 Discharged to facility without ventilator by day 14, and not readmitted between days 15- 28 Off ventilator by day 14 and discharged home between days 15-28

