3	Discharged to facility on ventilator by day 14 and not readmitted between days 15-28 Discharged to facility without ventilator by day 14 but readmitted between days 15-28 Off ventilator by day 14 and still in hospital between days 15- 28 Off ventilator by day 14 and discharged to facility between days 15-28 On ventilator > day 14 and discharged home between days 15-28
4	Discharged to facility on ventilator by day 14 and readmitted between days 15-28 On ventilator > day 14 and discharged to facility between days 15-28 On ventilator > day 14 and still in hospital between days 15- 28
5	Died in-hospital or designated for hospice care by day 28

Statistical methods for Aim 2a: The DOOR/RADAR probability represents the probability that a randomly selected patient who received the intervention has a better outcome than a randomly selected participant who received the standard reporting (control) accounting for antibiotic length of therapy. For each participant in an intervention cluster (ICU), the number of participants with a less desirable DOOR rank than that participant from the same ICU but during the control period will be determined. Results are then summarized across all 6 ICUs and the DOOR probability will be computed. Inverse probability weighting methodology using patient clinical characteristics may be applied to account for potential confounding.

In addition to the DOOR analyses just described, a two-dimensional analysis of the DOOR probability and difference in the mean duration of antibiotic use in the intervention and control groups will also be performed. Only subjects with non-missing DOOR and number of days on antibiotics will be included in these analyses. The horizontal axis will be the DOOR probability (probability of a more desirable outcome when assigned to intervention vs control) based on the 5-level ordinal DOOR outcome ignoring the duration of antibiotic use. The vertical axis is the difference in the means of the observed duration of antibiotic use (intervention minus control). A result in the lower right quadrant represents more desirable results for standard reporting (control), while a result in the upper left represents more

desirable for modified reporting (intervention). The other two quadrants represent tradeoffs for clinical outcomes and antibiotic use.

Aim 2b: Compare results of standard outcome analysis to those of DOOR analysis.

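### The DOOR probability rests on a strict count with no tie rule and no stated no-difference value; on the 5-level DOOR axis such a count sits at 40% or less when the arms are alike

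*SAP*

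**What the plan says.** The SAP describes two related analyses under Aim 2a.

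- **DOOR/RADAR.** The Strategy paragraph ranks patients by Table 2 "to obtain a 5-level ordinal outcome". It then gives two pairwise rules. If the ranks differ, the better rank wins. If they are equal, "the patient with a shorter course of antibiotics has the better outcome". Equal rank with equal duration is not covered. Under Statistical methods for Aim 2a, the target is the chance that a random intervention patient "has a better outcome than a randomly selected participant who received the standard reporting (control) accounting for antibiotic length of therapy". The computing step follows directly: for each intervention patient, "the number of participants with a less desirable DOOR rank than that participant from the same ICU but during the control period will be determined". The results are then combined over the six ICUs. No formula is given.
- **Two-dimensional analysis.** The SAP states: "The horizontal axis will be the DOOR probability (probability of a more desirable outcome when assigned to intervention vs control". This is "based on the 5-level ordinal DOOR outcome ignoring the duration of antibiotic use". Two quadrants are assigned to one arm or the other and two are called tradeoffs, but the SAP does not say at which horizontal value the quadrants divide.

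On durations, item 1a of the secondary outcomes adds: "For patients in category b, duration will be zero".

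**The concern.** All these definitions are strict: better, more desirable, less desirable. A pair with the same outcome satisfies none of them, and no other sentence says what such a pair contributes. With only five ranks, ties are common.

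Taken literally, the rule gives a probability whose value at no difference is not 50% and is not fixed in advance, because it depends on how often patients share a rank. Yet three parts of the plan need a reference value: the quadrant reading, the Aim 2a hypothesis of a better ranking, and the Aim 2b comparison of statistical and clinical significance. A reader who compares the reported probability with 50%, as its wording invites, would see a neutral intervention as unfavourable. A reader who picks another divider after seeing the data would be making a post hoc choice.

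**Working it through.** The SAP states no DOOR probability, null value or DOOR sample size, so there is no figure of its own to reproduce. The inputs from the SAP are the strict count, the five ranks, the exclusion of duration on the horizontal axis, the shorter-course rule in DOOR/RADAR, and zero duration for category b. All rank and duration distributions below are assumptions.

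**1. 5-level DOOR, arms alike.** Let p₁ to p₅ be the rank shares, the same in both periods. Tie share = Σp², and by symmetry the rest splits equally, so

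P(strictly better) = (1 − Σp²)/2.

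Σp² is smallest when all shares are 0.20: 5 × 0.04 = 0.20. The maximum is therefore (1 − 0.20)/2 = 0.40. This bound needs no assumption about the distribution. It holds within each ICU and for any weighted average over ICUs. A search over 200,000 random distributions found a maximum of 39.99%.

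| Ranks 1–5 (%) | Tie share | Strict | With half ties |
|---|---|---|---|
| 20/20/20/20/20 | 0.200 | 0.400 | 0.500 |
| 10/15/25/25/25 | 0.220 | 0.390 | 0.500 |
| 5/10/25/30/30 | 0.255 | 0.3725 | 0.500 |
| 5/5/20/40/30 | 0.295 | 0.3525 | 0.500 |
| 2/8/20/30/40 | 0.2968 | 0.3516 | 0.500 |

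**2. 5-level DOOR with a real benefit.** Assume intervention 14/23/25/17/21% and control 10/20/25/20/25%.

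- Better: 0.14×0.90 + 0.23×0.70 + 0.25×0.45 + 0.17×0.25 = 0.126 + 0.161 + 0.1125 + 0.0425 = 0.442.
- Tied: 0.014 + 0.046 + 0.0625 + 0.034 + 0.0525 = 0.209.
- Worse: 1 − 0.442 − 0.209 = 0.349.
- Better plus half tied: 0.442 + 0.1045 = 0.5465.

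The intervention wins more pairs than it loses (0.442 against 0.349), yet the strict value is below 50%.

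With a proportional-odds shift, a common odds ratio of 1.5 gives a strict value of 46.4% (equal ranks) or 44.3% (5/10/25/30/30%), against 56.4% or 56.3% with half ties. The strict value reaches 50% only at an odds ratio of about 1.89 or 2.08.

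**3. DOOR/RADAR, arms alike.** A tie now needs equal rank and equal duration. Assume that duration is independent of rank, that a share q has zero days, and that the rest is spread evenly over k durations. Then

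residual tie share = Σp² × [q² + (1 − q)²/k].

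- Equal ranks, q = 0.3, k = 12: 0.20 × (0.09 + 0.49/12) = 0.0262; strict null 0.4869.
- Equal ranks, q = 0.5, k = 12: 0.20 × (0.25 + 0.25/12) = 0.0542; strict null 0.4729.
- Ranks 5/10/25/30/30%, q = 0.5, k = 4: 0.255 × (0.25 + 0.0625) = 0.0797; strict null 0.4602.
- Ranks 5/10/25/30/30%, q = 0.7, k = 4: 0.255 × (0.49 + 0.0225) = 0.1307; strict null 0.4347.

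Over q from 0.3 to 0.7 the null is about 43% to 49%. The Power and Sample Size section assumes a "50% probability to receive antibiotic prescription in the control group", which is only a rough guide to q: patients in categories e and f may fall outside that 50%, yet their durations are recorded. At q = 0.5 the null is about 46% to 47%.

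**The case against.** The strongest reply is that silence is not a rule. The SAP says that a number will be determined and that a probability will then be computed. It does not say that tied pairs count for nothing, and the named method is cited to a source that may contain a tie convention. That source is not at hand, so the claim that the analysis will deny ties credit goes too far. What stands is that the only operational rule in the SAP is strict, its verbal definitions are strict as well, and following them as written gives the values above.

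Two other strong readings are tempting and are not supported.

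- **That 40% is the ceiling for every DOOR result.** The counting sentence follows the definition of DOOR/RADAR, where duration breaks most ties, and it is unclear whether the rank in that sentence already includes the tie-break. The 40% bound belongs to the 5-level DOOR only.
- **That the plan places a neutral intervention on the harmful side.** The SAP never names 50% as reference or divider. By the axis definitions a low value, on the left, is unfavourable to the intervention. The printed labels say the reverse: they assign lower right to control and upper left to the intervention. That contradiction is a separate matter.

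It is also fair to say that a strict probability is legitimate if reported with its reverse or judged against its own null. The SAP provides for neither. Finally, no test threshold or sample size depends on the DOOR probability, which limits the consequence.

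**Conclusion.** The point holds in a limited form. The SAP defines the DOOR probability by a strict count and states neither a tie rule nor a no-difference value. For the 5-level DOOR on the horizontal axis, such a count has a no-difference value of at most 40%. That bound is algebra. The values of 35% to 39%, and the odds ratio of about 1.9 to 2.1 needed to reach 50%, rest on assumed rank distributions and a proportional-odds shift. For DOOR/RADAR the displacement is smaller, with a no-difference value of roughly 43% to 49%, given assumed durations that are independent of rank.

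The apparent disadvantage arises only if the result is read against 50%, which is the reader's likely reference but not one that the SAP states. This should be corrected before the Aim 2 analysis. The primary outcome and the rest of Aim 1 are not affected.

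**What to change.** In Statistical methods for Aim 2a, define the DOOR probability as the proportion of within-ICU intervention–control pairs in which the intervention patient has the better outcome, plus one half of the proportion tied. Apply this to both versions. In the 5-level DOOR a tie is the same rank; in DOOR/RADAR it is the same rank and the same duration. State 50% as the no-difference value for both and as the vertical divider of the two-dimensional plot. The no-difference value is then exactly 50% for any rank distribution, and the probabilities in the two directions sum to 1.

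Separately, reconcile the quadrant labels with the axis definitions: with the axes as defined, lower right means a better DOOR probability and a shorter mean duration under the intervention.

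The cost is a sentence or two in the SAP. No extra data or patients are needed.
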